8.5.2 Secondary Efficacy Analyses

The secondary efficacy endpoints are:

- Change from baseline in CST as measured by Spectral Domain OCT (SD-OCT)
- Proportion of eyes with a ≥ 2 step improvement from baseline in DRSS score
- Change from baseline in BCVA letter count as measured by ETDRS
- Proportion of study eyes with ≥ 5 , ≥ 10 , and ≥ 15 BCVA letter change from baseline (gain and loss).

Change from baseline in BCVA letter count in the study eye at Week 24 and change from baseline in CST in the study eye as measured by SD-OCT at Week 16 and Week 24 will be analyzed using the same method described for the primary efficacy analysis. Note that change from baseline in CST will be in favor of KVD001 if the treatment difference is < 0 .

The proportion of study eyes with improvement of 2 or more steps on the ETDRS DRSS score between the sham procedure group and each of the KVD001 injection groups will be summarized by visit using discrete summary statistics, including 95% asymptotic normal CIs for each treatment group. The difference in proportions between each of the KVD001 groups and the sham procedure group will be analyzed at Week 16 and Week 24 using a Pearson's chi-squared test. 95% asymptotic normal CIs for the differences in proportions will also be calculated. Fisher's exact tests and exact CIs will be employed in cases of expected counts < 5 .

The proportion of study eyes with ≥ 5 , ≥ 10 and ≥ 15 BCVA letter change (gain and loss) between baseline and Weeks 16 and 24 will be analyzed using the same method described for the proportion of study eyes with improvement of 2 or more steps on the ETDRS DRSS score.

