3.1 General Study Design

This is a phase 2a, randomized, double-masked, sham-controlled, 3-arm study to evaluate the efficacy, safety, and tolerability of KVD001 Injection as monotherapy in adult subjects with ciDME who have had prior anti-VEGF treatment. Approximately 123 eligible subjects will be randomized into the study.

Subjects will undergo screening for fulfilling the inclusion and exclusion criteria in order to be eligible for this study. Eligible subjects will be stratified based on visual acuity and CST, and then randomly

assigned in a 1:1:1 ratio into the 3 groups described below. Stratified randomization will be performed centrally by visual acuity and CST at Day 1.

- KVD001 6 µg by IVT injection;
- KVD001 3 µg by IVT injection;
- Sham procedure.

Rescue intervention (e.g., anti-VEGF, focal/grid macular laser photocoagulation, IVT steroids) may be administered due to worsening DME (i.e., attributable to worsening DME and not another cause) if either of the following occurs and, where possible, after consultation with the Medical Monitor:

- During Treatment Phase
 - BCVA deteriorates 3 lines (15 letters) or more from baseline
 - CST worsening of >100 µm from baseline
- During Follow up Phase (i.e., after week 16)
 - BCVA deteriorates 3 lines (15 letters) or more from highest BCVA during treatment phase or baseline
 - CST worsening of >100 µm from lowest CST during treatment phase or baseline.

Subjects who receive a rescue intervention in the study eye will be discontinued from further study participation. The Week 24/Early Discontinuation (ED) evaluations should be collected prior to study discontinuation and prior to administration of the rescue medication. Details regarding the medications used as rescue treatment must be entered as concomitant medications for the respective study subject.

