3.2 Schedule of Visits and Assessments

The schedule of procedures is provided in **Appendix A**. The screening period will be up to 4 weeks. On the day of first study drug administration (Day 1), eligible subjects will be randomized to a 12-week, double-masked treatment period (a total of 4 doses given at approximately monthly intervals). Subjects will visit the study clinic on Day 1 and Weeks 4, 8, and 12 during the Treatment Phase. The visit window for these visits is -3 days to +7 days. All subjects will visit the clinic at Weeks 16, 20, and 24 after the last study drug administration or sham procedure for safety and ophthalmic assessments. The visit window for Weeks 16, 20, and 24 is ±7 days. For ED visits, the visits will be windowed according to the Protocol windows defined above and in **Table 1**.

Summaries and analyses utilizing timepoints will be completed using the nominal visit recorded in the electronic case report form (eCRF), except in the case of ED visits where the visit will be windowed to a scheduled visit using **Table 1**. In the case where a subject has a scheduled visit and a windowed ED

visit mapped to the same visit name, the observation closest to the planned study day will be used for analysis.

Table 1. Study Visit Windows for Early Discontinuation Visits

Scheduled Visit	Planned Study Day	Visit Window
Day 1	1	N/A
Week 4	28	15-42
Week 8	56	43-70
Week 12	84	71-98
Week 16	112	99-126
Week 20	140	127-154
Week 24	168	155-182

4. Study Treatments

Subjects will be randomized by the Interactive Response Technology (IRT) in a 1:1:1 ratio to 1 of the 3 treatment groups: KVD001 Injection (6 µg/eye or 3 µg/eye) or sham. Allocation to the treatments will be stratified by baseline BCVA (≤ 55 letters vs > 55 letters) and CST at Screening (≤ 450 µm vs > 450 µm) as determined by the study center.

1:1:1 randomization:

- KVD001 6 µg by IVT injection;
- KVD001 3 µg by IVT injection;
- Sham procedure.

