4.2 Masking and Unmasking

This is a double-masked study. Subjects, Investigators and site staff, the sponsor [REDACTED] [REDACTED] staff are masked to the treatment group assignments during the randomization process and for the duration of the study.

Under normal circumstances, the mask should not be broken. When medically necessary, an Investigator may need to determine what treatment has been assigned to a subject. The Investigator will contact the Sponsor with the details of the emergency unmasking request. The sponsor will make the final determination if the unmasking request will be granted. If granted, the unmasking information may be accessed through the use of an IRT system or provided by the unmasked designee. The Investigator must also indicate in source documents and in the eCRF that the mask was broken and provide the date, time, and reason for breaking the mask.

5. Sample Size and Power Considerations

The proposed sample size (41 per treatment group) will provide approximately 80% power to detect a difference in change from baseline of 5 letters between either of the KVD001 treatment groups and sham based on a two-sided, two-sample t-test with significance level 0.05 and assuming a pooled standard deviation (SD) of 7.5 letters.

6. Data Preparation

Data management procedures, including database design, selection of the data dictionary, and coding of all AEs and medications, will be performed [REDACTED]. All reported study data will be recorded on [REDACTED] eCRFs supplied [REDACTED]. Clinical personnel at the study center and [REDACTED] are responsible for ensuring that the protocol is followed and that the eCRFs are properly completed.

After data are entered into the clinical study database, electronic edit checks will be performed, including checks for missing data, out of range values, discrepancies within and across visits, and cross checks between different data tables. All data validation specifications and procedures are detailed in the Data Validation Manual (DVM), and manual data checks are documented in the Study Report Specifications (SRS). When the database has been declared to be complete and accurate, the database will be locked and treatment codes unmasked. Any changes to the database after that time can only be made with the approval of the Sponsor in consultation with Ora, Inc. [REDACTED]

All final analyses outlined in this document will be performed after:

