8.4 Data Analysis Conventions

All data analysis will be performed [REDACTED]. The final analysis will be performed after the study is completed and the database has been locked and released for unmasking. Statistical programming and analyses will be performed using SAS® Version 9.4 or higher.

Quantitative variables will be summarized using descriptive statistics including the number of observations (n), mean, SD, median, interquartile range (IQR), minimum, and maximum values. Means, medians, and confidence intervals (CIs) will be reported based on the level of precision for each variable. Summaries for discrete variables will include frequency counts and percentages. All percentages will be rounded to one decimal place (i.e., XX.X%). Change from baseline will be calculated as post-baseline value minus baseline value.

All efficacy analyses will be two-sided at a significance level of 0.05. The CIs for differences between treatment groups will be two-sided at 95% confidence. All p-values will be rounded to four decimal places; p-values less than 0.0001 will be presented as “<0.0001”; p-values greater than 0.9999 will be presented as “>0.9999.”

Extra assessments (i.e., unscheduled laboratory data or vital signs associated with non-protocol clinical visits or obtained in the course of investigating or managing AEs) will be included in listings, but not summaries. If more than one laboratory value is available for a given visit, the first valid observation will be used in summaries and all observations will be presented in listings. If the relative time is indeterminable, then the average of values at that visit will be used. It is noted that invalid laboratory data may not be used (from hemolyzed samples, mishandled samples, quantity not sufficient, or other conditions that would render values invalid).

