13.3 Secondary Analyses

The secondary endpoints are the following:

- Change from baseline in CST as measured by SD-OCT
- Proportion of eyes with a ≥ 2 step improvement from baseline in DRSS score
- Change from baseline in BCVA letter count as measured by ETDRS
- Proportion of SEs with ≥ 5 , ≥ 10 , and ≥ 15 BCVA letter gain from baseline and the proportion of SEs with ≥ 5 , ≥ 10 , and ≥ 15 BCVA letter loss from baseline.

Change from baseline in BCVA letter count as measured by ETDRS in the study eye and change from baseline in CST in the study eye as measured by the central image reading center (CIRC) using SD-OCT will be analyzed using the same method described for the primary efficacy analysis. Note that change from baseline in CST will be in favor of KVD001 if the treatment difference is < 0 .

The difference in proportion of SEs with improvement of 2 or more steps on the ETDRS DRSS score between each KVD001 injection dose and the sham and between the KVD001 Injection doses will be summarized by visit using discrete summary statistics, including 95% Clopper-Pearson CIs for each treatment group. The difference in proportions between each KVD001 Injection dose and the sham and between the KVD001 Injection doses will be analyzed using a Pearson's chi-squared test. 95% Clopper-

Pearson CIs for the differences in proportions will also be calculated. Fisher's exact tests and exact CIs will be employed in cases of expected counts <5.

The proportion of SEs with ≥ 5 , ≥ 10 and ≥ 15 BCVA letter change (gain and loss) between baseline and each post-baseline visit will be analyzed using the same method described for the proportion of SEs with improvement of 2 or more steps on the ETDRS DRSS score. Additionally, as an exploratory endpoint, the proportion of SEs with any BCVA letter loss between baseline and each post-baseline visit will be summarized similarly. Note that the categorizations of ≥ 5 , ≥ 10 and ≥ 15 BCVA letter change (gain and loss) or any BCVA letter loss are not mutually exclusive.

14. Safety Analyses

All safety data analyses will be performed on the safety population and displayed in subject data listings and summarized in tables. No statistical inferential testing will be performed for safety variables.

Safety endpoints include AEs, manifest refraction/BCVA, slip lamp biomicroscopy, dilated ophthalmoscopy, intraocular pressure (IOP), SD-OCT, EDTRS DRSS, physical exam findings, laboratory test results, and vital signs.

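### Binary secondary endpoints are tested without the randomisation strata; a stratified test would be a small gain in efficiency, conditional on the strata being prognostic

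*SAP*

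**What the plan says.** SAP Section 4 makes randomisation stratified: "Allocation to the treatments will be stratified by baseline BCVA" (55 letters or fewer against more than 55) and by CST (450 µm or less against more), which gives four cells. Subjects are "assigned in a 1:1:1 ratio into the 3 groups described below" (SAP 3.1).

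For the DRSS responder endpoint and the six BCVA gain and loss endpoints, SAP 13.3 says the difference in proportions "will be analyzed using a Pearson's chi-squared test". It adds that "Fisher's exact tests and exact CIs will be employed in cases of expected counts <5". Protocol 8.5.2 plans the same: the difference "will be analyzed at Week 16 and Week 24 using a Pearson's chi-squared test". Neither section names a stratification factor for these tests.

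Baseline is used elsewhere. The ANCOVA in Protocol 8.5.1.2 adjusts for baseline BCVA. The MMRM in SAP 13.2 adjusts for baseline BCVA and CST, and the same section plans subgroup analyses of the primary endpoint by stratification factor. The opening of SAP Section 13 is blacked out, so a general statement there cannot be excluded. The test paragraphs of 13.3 are legible.

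**The concern.** Stratified allocation balances the arms on BCVA and CST, so part of the outcome variation cannot contribute to the difference between arms. An unstratified test still counts that variation in its standard error. If the strata predict response, the standard error is too large, the true size falls below the nominal 5%, and some real differences in responder rates are missed that a stratified test would find. The letter gain and loss endpoints are cut-points of the same BCVA change that the primary analysis adjusts for baseline, so dropping every baseline factor here sits oddly with the rest of the plan.

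**Working it through.** **The plan's own figure.** SAP Section 5 states power for the primary endpoint only: "The proposed sample size (41 per treatment group) will provide approximately 80% power to detect a difference in change from baseline of 5 letters", with SD 7.5. Noncentrality = 5 / (7.5 × √(2/41)) = 3.02. Two-sided power at 0.05 is 84.7% by the t distribution, so 41 per arm is slightly generous (37 would give 80%). An unstated loss of about 10% would explain it, since 36.3/0.9 = 40.3, rounded up to 41. This does not bear on the present point. No power is stated for any binary endpoint.

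**Inputs from the documents.** 41 per arm, 1:1:1 allocation, 2 × 2 strata, two-sided 0.05, Pearson or Fisher rule.

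**Assumed inputs.** Cell shares 20/20/30/30%, permuted blocks of 6, sham rates 5% to 40%, an odds ratio of 1 to 10 per stratification factor, a treatment odds ratio common to all cells, and no dropout.

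**Formulas.**
- Pearson: z = (p₁ − p₀) / √[p̄(1 − p̄)(1/n₁ + 1/n₀)].
- CMH: z = Σ(aₛ − n₁ₛmₛ/Tₛ) / √Σ[n₁ₛn₀ₛmₛ(Tₛ − mₛ)/(Tₛ²(Tₛ − 1))]. Here, in cell s, aₛ is the number of responders on active, mₛ all responders and Tₛ all subjects.
- Under the null with balanced cells, the true variance is a fraction R = Σwₛpₛ(1 − pₛ) / [p̄(1 − p̄)] of what Pearson assumes. The size is then about 2[1 − Φ(1.96/√R)].

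**Worked case.** Sham rate 30%, odds ratio 3 per factor, cell rates 0.562, 0.300, 0.300 and 0.125:

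R = (0.2×0.562×0.438 + 0.2×0.3×0.7 + 0.3×0.3×0.7 + 0.3×0.125×0.875) / 0.21 = 0.187/0.21 = 0.891.

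Size ≈ 2[1 − Φ(1.96/0.944)] = 3.8%. Simulation gives 4.0%.

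**Simulation.** 20,000 trials per setting, one dose arm against sham. The ranges cover three settings: 20 vs 48%, 30 vs 60% and 40 vs 70%.

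| Odds ratio per factor | Size, planned (%) | Size, CMH (%) | Power, planned (%) | Power, CMH (%) | CMH gain (points) |
|---|---|---|---|---|---|
| 1 | 5.1–5.3 | 5.1 | 78.0–80.1 | 77.6–79.5 | −0.8 to −0.4 |
| 2 | 4.3–4.9 | 4.7–5.3 | 79.2–80.1 | 80.2–80.8 | +0.8 to +0.9 |
| 3 | 3.7–4.1 | 4.8–5.0 | 79.0–81.2 | 81.7–83.7 | +2.5 to +2.7 |
| 5 | 2.8–3.5 | 4.8–5.1 | 80.3–82.1 | 85.7–87.6 | +4.9 to +5.5 |
| 10 | 1.7–2.0 | 4.7–4.9 | 82.3–84.2 | 90.7–92.3 | +7.9 to +8.4 |

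The planned test's power never falls below the ordinary unstratified formula (77.3%, 79.0% and 79.0% in the three settings). The loss is relative to a stratified test only.

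**Rare outcomes.** Fisher takes over when the pooled rate is below 5/41 = 12.2%. With non-prognostic strata, the planned rule has size 1.0% at a 5% rate and 2.9% at a 10% rate, against 4.1% and 4.9% for CMH. Plain Pearson gives 4.4% and 5.1%, so at low rates the main cause is the Fisher switch, not the omitted strata. These CMH figures are for the large-sample test. A stratified exact test is also discrete and was not simulated.

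**The case against.** The strongest reply is that the effect is conditional and the documents supply no condition. They give no response rate and no stratum effect. If BCVA and CST do not predict response, CMH is slightly worse. The endpoints are secondary, the trial is declared exploratory with no multiplicity adjustment (SAP 8.5), and no power is claimed for them. All of this stands, and it limits the point to efficiency.

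A reader might infer that the planned test gives wrong error rates. It does not: size is at or below nominal, to within about 0.3 points.

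A reader might also infer a large loss of power. That takes extreme stratum differences. With 35% of subjects in the low-BCVA stratum and a treatment log-odds effect of 1.2, three sets of assumed control rates (low BCVA, then high BCVA, each in two CST cells) give Pearson against CMH power as follows (12,000 trials each):
- 40/50/20/30%: 72.2% vs 73.1%.
- 50/60/12/22%: 60.0% vs 66.2%.
- 60/70/6/12%: 34.7% vs 53.4%.

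The BCVA odds ratio in the last set is (0.60/0.40)/(0.06/0.94) = 23.5 in one cell pair and (0.70/0.30)/(0.12/0.88) = 17.1 in the other. Nothing in the documents supports rates like these. Most of the fall in Pearson power across the sets comes from the marginal risk difference shrinking from about 27 to 17 points; CMH power falls too.

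A ceiling or floor on letters might seem to guarantee prognostic strata. Eligibility is 19 to 73 letters (Protocol 4.1). An eye at 19 can still lose 15, and an eye at 73 that gains 15 reads 88. The documents show no limit that would bind. Weaker prognosis remains plausible for the letter endpoints; for DRSS the documents point to no mechanism.

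Sparse cells are not a reason against CMH. The shares above give about 8 or 12 subjects per arm per cell (41 × 0.2 and 41 × 0.3), and CMH held its size at sham rates of 20 to 40%.

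**Conclusion.** The point holds as a minor efficiency improvement. The planned Pearson or Fisher test is valid but does not use the randomisation strata. It gives up power, relative to a stratified test, only as far as those strata predict the outcome. At sham rates of 20 to 40%, CMH costs up to about 1 point if they do not. It gains under 1 point at an odds ratio of 2 per factor, about 2.5 at 3, about 5 at 5 and about 8 at 10. Which of these applies cannot be settled from the documents. The figures rest on the assumed cell shares, block size, response rates and common treatment odds ratio, with complete data in 41 per arm.

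**What to change.** In SAP 13.3:
- Replace the Pearson test with a CMH test over the four randomisation cells, for each pairwise comparison.
- Report the Mantel-Haenszel risk difference with its 95% CI. An interval for the difference needs naming in any case, because the Clopper-Pearson interval now specified is a method for a single proportion.
- If a cell has no subjects in one arm, pool over CST. Otherwise that cell's subjects contribute nothing.
- For low counts, use a stratified exact test instead of unstratified Fisher.
- Define the cells by the stratum recorded in the IRT. SAP 3.1 and Protocol 4.5.2 place the CST stratifier at Day 1, while SAP 4 and 4.1 and Protocol 8 place it at Screening. This should be reconciled first.

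The cost is SAP wording and a small programming change, with no new data. The downsides are the pooling rule and up to about 1 point of power if the strata turn out not to be prognostic.

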14.1 Adverse Events

An AE is defined as any untoward medical occurrence associated with the use of an investigational product (IP) in humans, whether or not considered IP-related. AEs starting on or after the date of first exposure to study drug and up to 28 days after last injection will be considered treatment-emergent adverse events (TEAEs). AEs with unknown onset dates will be counted as a TEAE. All AEs will be assigned a severity grade of mild, moderate, or severe. Their relationship to study drug will be classified as suspected or not suspected. TEAEs with a missing relationship to study treatment will assume greatest relationship to study treatment (suspected). Only suspected TEAEs are considered as treatment-related. TEAEs with missing severity grades will be categorized as severe for tabulation of TEAEs by severity. The expectedness of an AE will be classified as unexpected, expected or not applicable (not applicable for AEs unrelated to IP). Documentation of AEs will include onset date, location (right eye [OD], left eye [OS], both eyes [OU], not ocular), severity, action(s) taken, relationship to study drug, expectedness, outcome, resolution date, and seriousness. All AEs will be coded using MedDRA classifications with reference to SOCs and PTs (MedDRA version 20.1).

An AE is considered serious if, in the view of either the investigator or sponsor, it results in any of the following outcomes:

- Death
- A life-threatening AE
- Inpatient hospitalization or prolongation of existing hospitalization

- A persistent or significant incapacity or substantial disruption of the ability to conduct normal life functions
- A congenital anomaly/birth defect
- Medically Significant.

Important medical events that may not result in death, be life-threatening, or require hospitalization may be considered serious when, based upon appropriate medical judgment, they may jeopardize the subject and may require medical or surgical intervention to prevent one of the outcomes listed above.

Overall summaries of AEs will be presented showing:

- Number of AEs and number of subjects with any AEs;
- Number of TEAEs and number of subjects with any TEAEs;
- Number of treatment-related TEAEs and number of subjects with any treatment-related TEAEs;
- Number of SAEs and number of subjects with any SAEs;
- Number of treatment-emergent SAEs and number of subjects with any treatment-emergent SAEs;
- Number of subjects with TEAEs leading to premature discontinuation;
- Number of subjects with TEAEs leading to death; and
- Number of subjects with TEAEs by maximum severity.

Overall summaries of AEs will be presented for the following classes of events:

- All AEs (ocular & non-ocular)
- Ocular events for each eye (study eye and fellow eye)
- Non-Ocular events

Frequencies and percentages of subjects with TEAEs, serious TEAEs, TEAEs leading to study drug discontinuation, and treatment-related TEAEs will be provided by treatment group by SOC and PT.

Furthermore, summaries will be given of subjects with TEAEs:

- by SOC, PT, and maximum severity;
- by SOC, PT, and strongest relationship;
- by SOC and PT for SAEs;
- by SOC and PT for TEAEs related to study drug; and
- by SOC, PT, and time of onset (i.e., Day 1 to Week 4 [Days 1-28], > Week 4 to Week 8 [Days 29-56], > Week 8 to Week 12 [Days 57-84], > Week 12 to Week 16 [Days 85-112], > Week 16 [> Day 112]).

Separate analyses will be performed for ocular specific AEs, and all AEs (including systemic).

Summaries of preferred terms (without regard to SOC) will be presented for TEAEs and the most frequent TEAEs (occurring in $\geq 5\%$ of patients treated with KVD001 6 μg or KVD001 3 μg).

Post-treatment AEs, defined as AEs that started or worsened more than 28 days after last injection, will also be summarized.

Subject listings of all AEs including verbatim text will be provided as well as listings of deaths, SAEs, and AEs causing premature discontinuation of study drug.

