--	--

	
The proportion of study eyes with improvement of 2 or more steps from baseline on the ETDRS DRSS score between the sham procedure group and each of the KVD001 Injection groups will be summarized by visit using discrete summary statistics, including 95% asymptotic normal CIs for each treatment group. The difference in proportions between each of the KVD001 Injection groups and the sham procedure group will be analyzed at Week 16 and Week 24 using a Pearson's chi-squared test. The 95% asymptotic normal CIs for the differences in proportions will also be calculated. Fisher's exact tests and exact CIs will be employed in cases of expected counts <5.
 
The proportion of study eyes with ≥ 5, ≥ 10 and ≥ 15 BCVA letter change from baseline (gain and loss) at Weeks 16 and 24 will be analyzed using the same method described for the proportion of study eyes with improvement of 2 or more steps from baseline on the ETDRS DRSS score.
 
Safety Variables:
 
AEs will be coded using the MedDRA dictionary. Frequencies and percentages of subjects with treatment-emergent adverse events (TEAEs), serious TEAEs and TEAEs causing premature discontinuation will be provided by treatment group. An AE is treatment emergent if it occurs or worsens after the first dose of randomized study treatment. Furthermore, frequencies will be given of subjects with TEAEs by system organ class (SOC) and preferred term (PT); by SOC, PT and maximal severity; by SOC, PT and strongest relationship; by SOC and PT for SAEs; and by SOC, PT and day of onset. Separate analyses will be performed for ocular specific and all AEs (including systemic).
 
Other safety endpoints including manifest refraction/BCVA, slit lamp biomicroscopy, dilated ophthalmoscopy, IOP, SD-OCT, ETDRS DRSS, physical exam findings, laboratory test results, and vital signs will be summarized by treatment group and visit using descriptive statistics. Changes or shifts from baseline will also be summarized where appropriate. For assessments performed by eye, study eye and fellow eye will be summarized separately.

--	---

LIST OF STUDY PERSONNEL

Sponsor

KalVista Pharmaceuticals, Ltd.
[name]
[name]
[name]
United Kingdom

[Redacted]
[Redacted]
[Redacted]
[Redacted]
[Redacted]
[Redacted]
[Redacted]
[Redacted]

Contract Research Organization

Ora, Inc.
[name]
[name]
USA

[Redacted]
[Redacted]
[Redacted]
[Redacted]

Adverse Event Reporting

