8.6.1 Adverse Events

AEs will be coded using the MedDRA dictionary. Frequencies and percentages of subjects with treatment-emergent adverse events (TEAEs), serious TEAEs, and TEAEs causing premature discontinuation will be provided by treatment group. An AE is treatment emergent if it 1) occurs after the first dose of randomized study treatment or 2) if it is present prior to receipt of randomized study treatment but worsens in severity or increases in frequency after the first dose of randomized study treatment. Furthermore, frequencies will be given of subjects with TEAEs by system organ class and preferred term; by system organ class, preferred term and maximal severity; by system organ

class, preferred term and strongest relationship; by system organ class and preferred term for SAEs; and by system organ class, preferred term, and day of onset. Separate analyses will be performed for ocular specific and all AEs (including systemic). AEs will be classified by System Organ Class (SOC) and preferred term in the MedDRA coding dictionary. AEs will be tabulated both as the total events (regardless of relationship to treatment) and as drug-related events. The number of subjects with one or more events versus no events will be calculated for each treatment.

Subject listings of all AEs will be provided as well as listings of deaths, SAEs, and AEs leading to discontinuation.

The following summaries will be provided:

- Relationship between AE SOC and verbatim text;
- On-treatment AEs: number and percentage of subjects reporting each AE, each AE leading to withdrawal, each SAE, each drug-related SAE, each fatal AE, and most frequent by treatment;
- Post-treatment AEs: number and percentage of subjects reporting each AE;
- Listing of all AEs;
- Summary of Most Frequent AEs.

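### SAP 14.1 narrows the protocol's treatment-emergent AE definition to 28 days after the last injection, omits worsening, and does not declare the change in Section 16

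*SAP*

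**What the plan says.** Protocol Synopsis, Safety Variables: "An AE is treatment emergent if it occurs or worsens after the first dose of randomized study treatment". Protocol 8.6.1 gives the same rule in two limbs. One is onset after the first dose. The other makes an AE treatment-emergent "if it is present prior to receipt of randomized study treatment but worsens in severity or increases in frequency after the first dose". Neither place sets an end date.

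SAP 14.1 instead counts "AEs starting on or after the date of first exposure to study drug and up to 28 days after last injection", and adds "AEs with unknown onset dates will be counted as a TEAE". Worsening is not part of this definition. It appears only in the SAP's definition of post-treatment AEs, which are those starting or worsening beyond the 28-day cut. SAP 14.1 also states "Only suspected TEAEs are considered as treatment-related", and asks for TEAEs by onset period with these last two bands: "> Week 12 to Week 16 [Days 85-112], > Week 16 [> Day 112" (days).

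SAP Section 1 says the SAP's methods replace the protocol's. SAP Section 16 lists six departures from the protocol: FAS, PPS, prior medications, between-dose comparisons, Clopper-Pearson intervals, and any letter loss. The TEAE definition is not among them.

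**The concern.** Local and systemic safety and tolerability is the trial's only secondary objective (Protocol 2.2). AEs are recorded through Week 24 (Protocol Table 2) and monitored until resolution or Week 24 (Protocol 6.2.1.8). A reader who knows the protocol definition would take the TEAE and treatment-related rates by arm to cover that whole period. Under the SAP they stop at about Week 16, and earlier for a subject whose dosing stops early, and Section 16 gives no notice of it.

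Three things follow from the narrower label:

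- A suspected AE with a known onset after the cut-off is excluded from the treatment-related counts.
- Late AEs leave the TEAE tables by severity, relationship and onset, and the counts of TEAEs leading to discontinuation or death.
- An AE that began before dosing and worsened during treatment has no place in the TEAE definition.

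**Working it through.** **Inputs.** SAP Table 1 (Section 3.2): Week 12 is planned Day 84 and Week 24 is planned Day 168. Visit windows (SAP 3.2, Protocol 3.1): -3 to +7 days at Week 12, ±7 days at Week 24. Last onset band (SAP 14.1): after Day 112.

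**End of the TEAE window** = day of last injection + 28.

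- Planned: 84 + 28 = Day 112, exactly where the last onset band begins.
- If 28-day spacing is counted from Day 1, the fourth injection is on Day 1 + 3 × 28 = Day 85, and the window ends on Day 113.
- Week 12 at its limits: 84 - 3 = Day 81 gives Day 109; 84 + 7 = Day 91 gives Day 119.

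**Share of follow-up outside the window**, fully dosed subject followed to Week 24:

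| Case | Calculation | Share |
|---|---|---|
| Planned days | (168 - 112)/168 = 56/168 | 33.3% |
| Latest Week 12, earliest Week 24 | (161 - 119)/161 = 42/161 | 26.1% |
| Earliest Week 12, latest Week 24 | (175 - 109)/175 = 66/175 | 37.7% |

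If dosing stops after the first, second or third injection, the window closes at Day 1 + 28 = 29, 28 + 28 = 56 or 56 + 28 = 84. The documents do not say how many subjects would stop dosing and stay in follow-up, so no trial-wide figure follows.

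**Days of the last onset band (Days 113 to 168, 56 days) that the TEAE rule can reach:**

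- Planned Day 84: 112 - 112 = 0 days.
- Day 85 counting: 113 - 112 = 1 day.
- Latest Week 12 dosing in the fixed-week window: 119 - 112 = 7 days (Days 113 to 119), or 7/56 = 12.5%.
- If +7 days were allowed on each interval: Day 1 + 3 × 35 = Day 106, window end Day 134, and 134 - 112 = 22 days, or 22/56 = 39%. The week-based columns of Protocol Table 2 favour the fixed-week reading.

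**Treatment-related events.** Protocol 8.6.1 says in general terms "AEs will be tabulated both as the total events (regardless of relationship to treatment) and as drug-related events", with no time limit. Under the SAP, an AE starting after the cut-off and judged suspected is not a TEAE, so it is not treatment-related.

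**Worsening.** Take an AE recorded between consent and first dose that worsens during dosing. If it stays on its original record, its start date precedes exposure, so it is not a TEAE. It did not worsen beyond the 28-day cut, so it is not post-treatment either. Protocol 6.2.1 treats a clinically relevant deterioration in a clinical finding as an AE to be recorded. If sites enter that as a new AE, the gap closes in practice. The eCRF instructions are not in these documents.

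**The case against.** The strongest defence is that 28 days is not arbitrary. SAP 12.2 uses the same period as the at-risk time for on-treatment AEs, and it equals one planned dosing interval. Protocol 8.6.1 itself separates on-treatment from post-treatment AEs and lists drug-related SAEs, withdrawals and fatal events under on-treatment only. For the later period it asks just for "Post-treatment AEs: number and percentage of subjects reporting each AE". All of this stands. It supports 28 days as an on-treatment period. It does not support giving that subset the TEAE name, which the protocol defines without an end date; SAP 12.2 itself calls the period on-treatment.

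Several stronger readings are tempting but not supported:

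- **Late AEs are lost.** They are not. They stay in the all-AE and SAE counts, in Table 14.3.1.2.9 by SOC and PT, and in the listings. Ocular AEs are also counted by eye in Table 14.3.1.1.2, and ocular SAEs are tabulated by eye in Table 14.3.1.2.4. The protocol does not require by-eye AE tables for the late period.
- **The SAP flatly contradicts itself on the last onset band.** The band is empty only if the last injection is on Day 84 or earlier. It can be read as an open-ended final category for late dosing, and Protocol 7.1 foresees dosing outside windows. It is nearly unused, not impossible.
- **Silence in SAP Revision 01 shows concealment.** That log records changes since SAP version 1.0, so it says nothing about departures from the protocol. Only Section 16 is relevant.

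The SAP's rules for unknown onset, missing relationship and missing severity are conservative, but they do not bring back a late AE with a known date.

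**Conclusion.** The point holds as an undeclared narrowing of a safety definition, with a direct effect on the TEAE and treatment-related rates. It should be fixed. On planned days, 33% of a fully dosed subject's follow-up to Week 24 (26% to 38% across fixed-week visit windows) lies outside the TEAE window. A reader might infer that a third of AEs are dropped. The documents give no late event rate, so no share of events can be stated. Subjects who are rescued or withdraw leave the study and contribute fewer excluded days, or none.

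The missing worsening limb is a real textual omission. It has a practical effect only if worsening is not entered as a new AE. The safety analysis is descriptive, every AE is still listed, and no efficacy result changes.

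**What to change.** **Preferred.** In SAP 14.1, define an AE as treatment-emergent if it starts, or worsens in severity or frequency, at any time from first dose to the last study visit. Use the 28-day period, in line with SAP 12.2, only to divide TEAEs into on-treatment and post-treatment, with worsening in both parts. Any suspected TEAE then counts as treatment-related, and the last onset band covers Days 113 to 168 on planned timing. State how worsening is identified, for example as a new record dated at the worsening.

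**Alternative.** Keep the 28-day TEAE window, but:

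- declare it in Section 16;
- add the worsening limb;
- remove the TEAE restriction from the treatment-related rule;
- relabel or drop the onset band after Week 16.

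**Cost.** SAP wording and one derivation flag, plus at most an eCRF completion note. No new assessments. TEAE and treatment-related counts would be somewhat higher under the first option, and treatment-related counts somewhat higher under the second.
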